5.2 Secondary outcomes

- The pain response measured by the AUPC (NRS every 10 minutes during electrical stimulation) will be used for further comparison of the two different treatment interventions every participant recieves during the study. We compare the participants received a education about placebo to the non prior educated participants.
- 2. Hyperalgesia and allodynia will be measured analogously to the NRS as above.
- 3. Saliva concentration of cortisol, measured at baseline, 30, 60 and 100 minutes after pain induction.

5.3 Safety outcomes

General patient well-being will be assessed by a consultant anaesthesiologist.

5.4 Safety and Tolerability Assessment

The participant will be under constant supervision during the course of stay by anaesthetist staff.

6. Investigational medical product

Placebo:

The placebo will be applied via a 5ml syringe containing 5ml of saline 0.9%. Application is done via a venous access inserted at the beginning of the experiment.

7. Study design

7. 1 Subjects and Study Center:

Type and number of study participants: 32 healthy male volunteers.

Number and location of participating centers: monocenter study, University Hospital Basel, Switzerland

7.2 General study design and justification of design

An assessor-blinded, randomized crossover study design will be applied. Each patient will undergo each of the two treatments (A-B) listed below. Furthermore, patients will be randomized to either receive placebo education or to not receive placebo education (e.g. B_1 = placebo education; B_2 = no placebo education). In other words, each patient will receive one of the two following treatment sets: either (A, B_1) or (A, B_2); the individual components of these sets will be randomized.

TREATMENT	General (visible)	Open drug application	
A→ No treatment	Infusion RL	No	
intervention	Infusion rate: 100ml/h		

B _{1,2} →Open-label	Infusion RL	OLP
Placebo alone	Infusion rate: 100ml/h	

Table 1: Overview study interventions

In each treatment the patient will receive a standard infusion containing only Ringer lactate (RL) infused at a rate of 100ml/h. The purpose of this infusion is simply to keep venous access.

To avoid any systematic bias the assignment of the study groups will be performed in a balanced randomized manner. To control for excitement and habituation effects we operate the interventions in a randomized order in every participant.

The participants are recruited by an advertisement on the University of Basel homepage and eligible volunteers will be included on a "first come, first served" basis.

Study participants are orally and written informed about study aims and interventions before the first assessment.

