7.5 Experimental design

Acute pain will be induced through electrical stimulation in an established model first described by [name] et al.[16]. (For detailed experimental setup cp. Chapter 7.6-7.7)

Before the first intervention participants will be randomized to:

- 1) A placebo education group
- 2) A non-placebo education group

Participants in both groups will undergo the pain model two times. Every participant will receive treatment as follows in a sequential cross-over design (cp fig. 1).

[figure not shown]

Figure 1: Experimental design

During every experiment levels of saliva cortisol levels are collected at baseline, 30min, 60min and 100min after pain induction (cp. Fig. 4).

A washout period of two weeks well be instituted to prevent contamination (cp. Fig 1).

Randomization as well as preparation and application of the hidden and not hidden study medication will be executed by study stuff not involved in assessments during the intervention. During the individual experiment pain scores, hyperalgesia and allodynia will be assessed and documented by an investigator blinded to the treatment group.

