9.4 Subject Withdrawal

Subjects may withdraw from the study at any time and for any reason (stating reason is not required). If patients elect to do so, data will be anonymized and no further analyses conducted. To replace this study drop-out, an additional patient will be recruited. Drop outs will be reported in the final publication.

The following reasons result in withdrawal:

- AE challenging the health of the subject if continuing the study
- Severe protocol violations
- Administrative troubles

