11.2 Determination of sample size

Sample size has been determined by a Wilcoxon signed-rank test for the AUPC for Treatments A and B. The AUPC is the product of the NRS x Time. 7 measurements of NRS will be made in total, one every ten minutes. We expect the area under the curve to be 50 NRSxminutes based on a general difference of 1 NRS point and some time for the effect to fully develop. We expect the standard deviations in both groups to be 1 NRS or 60 NRS*min. Using a t-test with a 20% mark-up for non-parametric data we have arrived at a required number of patients of 22. However since 20-30% of participants can be expected to be non-responders to placebo [38] and expecting 10% drop out we have arrived at a total number of patients to be recruited of 32.

11.3 Statistical criteria of termination of the trail:

Upon completion. With such a small sample size, no interim analysis will be conducted.

11.4 Planned Analyses, Datasets, and Analysis Populations:

For the first hypothesis (AUPC for $B_{1/2}$ vs. A) we will conduct a Wilcoxon signed-rank test. Additionally, we conduct a mixed effects model using the AUPC as the dependent outcome and the treatment, the session order (e.g. Treatment B before Treatment A) time during electrical stimulation (in minutes), and finally the individual. This will allow for a more differentiated analysis accounting for temporal and sessional habituation in explaining the treatment effect.

For the effect of education, we will compare the AUPC of: Treatment B_1 vs Treatment B_2 , again by a Wilcoxon signed-rank test.

The outcomes hyperalgesia and allodynia, as well as biomarkers will be examined analogously to the respective comparisons with the AUPC.

11.8 Interim analysis:

Given the small sample size and limited time, no interim analysis will be conducted.

11.9 Safety analysis:

None. However, patients will be under the continuous surveillance of anesthesiology staff.

11.10 Deviation(s) from the original statistical plan:

The statistical plan will be published prior to commencement on clinicaltrials.gov. Any deviations from the statistical plan will be reported and justified in the final report.

11.11 Handling of missing data and drop outs:

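### Balance of session order is not stated, overall or within education groups, so a chance imbalance can move both planned comparisons by a fraction of any session effect

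*Combined protocol and SAP*

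**What the plan says.** Section 7.2 describes two random steps. On groups it says "To avoid any systematic bias the assignment of the study groups will be performed in a balanced randomized manner". On order it says "To control for excitement and habituation effects we operate the interventions in a randomized order in every participant", and of the two treatment sets (A with B1, A with B2) that "the individual components of these sets will be randomized". Section 7.5 presents the education allocation as a separate step: "Before the first intervention participants will be randomized to" an education or a non-education group. The readable text gives no 1:1 ratio for A-first and B-first, no blocks, and no stratification of order by education group. It does not define study groups.

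Section 9.4 replaces drop-outs ("To replace this study drop-out, an additional patient will be recruited") without saying which group or order the replacement receives.

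For A vs B, section 11.4 says "we will conduct a Wilcoxon signed-rank test". It adds a mixed model whose terms include "the session order (e.g. Treatment B before Treatment A) time during electrical stimulation (in minutes), and finally the individual", intended to account for habituation between sessions. The synopsis repeats that the model will account for treatment order. For B1 vs B2, section 11.4 names a Wilcoxon test and no model.

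**The concern.** The plan itself treats a change in pain response from session 1 to session 2 as plausible: it cites habituation as the reason for randomising order, and again as a reason for the mixed model. Random order protects on average over many trials. In one trial of 32 men, the protection is only as good as the realised split.

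If more men receive B second than first, part of the session effect is counted as placebo effect, and the reverse split hides part of the placebo effect. If the education groups differ in their order mix, the same leakage enters B1 vs B2. That comparison has a second exposure: education is given once, before the first session (section 7.4), and the washout is at least two weeks (synopsis). Educated men who start with A therefore receive placebo at least two weeks further from their education.

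**Working it through.** **Inputs from the plan (11.2):** planned effect 50 NRS×min; SD per condition 60; N = 22 before allowances, 32 recruited. **Assumed, because not stated:** two-sided 5% level, 90% power, within-man correlation 0.5 (so SD of the paired difference = 60·√(2·(1−0.5)) = 60), simple randomisation of order, 16 men per education group, and a session effect π (the change from session 1 to session 2) of 10 to 60 NRS×min.

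**Plan's own figure.** A paired t-test with effect 50 and SD of difference 60 needs 17.2, so 18 men; 18 × 1.2 = 21.6, so 22. Then 22/0.75 = 29.3 (29) and 29/0.9 = 32.2 (32). The plan's numbers are consistent with an SD of difference of 60, though other assumptions come close: correlation 0.25 with 80% power gives 23.

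**Size of the shift.** With true effect τ, the expected B − A difference is τ + π in an A-first man and τ − π in a B-first man. The mean over all men is τ + π·(A-first − B-first)/N. At 20:12 the fraction is 8/32 = 0.25. For B1 vs B2 the shift is π times the difference between groups in the share receiving B second; a difference of 4 men in 16 again gives 0.25. In both cases the fraction has mean 0 and SD 1/√32 = 0.177.

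**Probability of imbalance.**
- Binomial(32, 0.5): exactly 16:16, 0.14; 12:20 or worse, 0.215; 10:22 or worse, 0.050.
- Two independent Binomial(16, 0.5): counts differ by 4 or more, 0.215; by 6 or more, 0.050.
- Order forced to 16:16 overall but not within education group (hypergeometric): counts differ by 4 or more, 0.289.

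**Effect on the unadjusted signed-rank test** (32 men, 4,000 simulated trials per cell, true effect 50 for power):

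| π | Shift at 12:20 (% of 50) | Type I error given 20:12 | Power given the unfavourable 12:20 | Power, simple randomisation | Power, forced 16:16 |
|---|---|---|---|---|---|
| 10 | 2.5 (5%) | 0.056 | 0.99 | 0.993 | 0.994 |
| 20 | 5 (10%) | 0.057 | 0.97 | 0.990 | 0.994 |
| 30 | 7.5 (15%) | 0.067 | 0.94 | 0.979 | 0.989 |
| 60 | 15 (30%) | 0.088 | 0.57 | 0.858 | 0.940 |

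Over all simple randomisations, type I error is 0.047 to 0.053 for these session effects.

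**Precision.** The variance of the mean difference is 60²/32 + π²/32 under simple randomisation and 60²/32 when balanced. At π = 30 this is 112.5 + 28.1 = 140.6 against 112.5, so balancing lowers it by 20%. At π = 60 it is 225 against 112.5. The unadjusted test does not realise all of this gain, because its error term still contains the session effect: with 16:16 forced, its type I error drops to 0.030 at π = 30 and 0.004 at π = 60.

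**What the mixed-model term does.** A label for A-before-B or B-before-A is constant within a man, so it cancels from his B − A difference and leaves the shift in place. A session-number term estimates τ as the average of the two sequence means, ½[(τ + π) + (τ − π)] = τ, whatever the split. Its variance is (60²/4)·(1/n₁ + 1/n₂): 112.5 at 16:16 and 900·(1/20 + 1/12) = 120 at 20:12.

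**The case against.** Four stronger readings are tempting, and the documents support none of them.

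- **That balance is required for education only.** Study groups is undefined and the sentence sits beside the one on order, so it may cover sequence too. A random order for each man is compatible with a blocked list, and section 7.11 mentions a stored randomisation code. The design figure in section 7.5 and part of the synopsis could not be read in the copy reviewed. The 22% is therefore conditional on simple randomisation.
- **That the design is biased.** It is not: order is random, the estimate is unbiased over randomisations, and type I error is held.
- **That the whole habituation effect enters the contrasts.** Only the imbalance fraction does, with an SD of about 18% of the session effect.
- **That the plan ignores order.** It adds a mixed model with an order term for A vs B. If that term means session number, the model removes the shift.

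Two further points stand. Setting the current to NRS 6 in each session, with three further increases (section 7.7), and the two-week washout probably make the session effect smaller; its size is not given. And forcing balance alone adds little power for the primary test at small session effects: nothing visible at 10 to 20, and 0.98 to 0.99 at 30.

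What remains is that balance of order is not stated, the mixed model is additional to the signed-rank test, its example reads as a sequence label, and B1 vs B2 has no order adjustment named.

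**Conclusion.** The point holds as a weakness in allocation and adjustment. It is not a systematic bias. Under simple randomisation of 32 men, roughly one trial in five has a 12:20 split or worse, and roughly one in five has education groups differing by 25 points or more in order mix. The resulting shift is 25% of a session effect of unknown size: negligible if that effect is near 10 NRS×min, material if it is near 60. B1 vs B2 is the more exposed comparison, because no planned analysis accounts for order there. Balancing order only overall does not protect it (29%). These figures rest on the assumed session effect, an SD of difference of 60, and simple randomisation. If the actual list is already blocked by order within education group, the imbalance probabilities fall away and a statement of the method is enough for the allocation; the analysis terms would still need defining.

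**What to change.** 1. In 7.2 and 7.5, replace the two separate steps with one computer-generated list of four cells (educated or not, by A-first or B-first) in permuted blocks, giving 8 men per cell at 32. At 8 per cell the imbalance fraction is zero in both contrasts.
2. In 9.4, state that a replacement takes the cell of the man replaced.
3. In 11.4, define the mixed-model order term as session number (first or second), so that the precision gained by balancing is realised.
4. In 11.4, account for order in B1 vs B2. The two sets are different men, so a between-group rank comparison stratified by order would serve, or a linear model with education group and the session in which B was given.

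The cost is one new list and a few sentences. It needs no extra participants, visits or staff. If the existing list already does this, saying so covers the first item.

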7.3 General participant information

Every participant is informed that he will receive an open label placebo during one of the two interventions and no treatment in the other intervention. In addition, every participant receives the explanation that a placebo is an inactive substance therefore contains no active ingredient. A general explanation of the term "placebo effect" is also given to every volunteer.

7.4 Participant education in in the placebo education group

The participants randomized to the PEG will receive additionally an education about placebos prior to the first intervention with following content (adopted from prior open label placebo studies [1, 2] and adapted to the current study design):

- A) Showing data about the possible strength of a placebo effect. Abstracts of prior placebo investigations are presented [1, 2].
- B) The possible automatically response of the body to placebo application is discussed. Pavlov dogs experiments and effects of prior studies are presented to the volunteer.
- C) Education that a positive attitude towards placebos can be helpful but is not necessary for the placebo effect [8-10].
- D) A television news report of an open label placebo education is shown to the participant at the end of the education session. (excerpted from: http://www.nbcnews.com/video/nightly-news/40787382#40787382). To ensure proper understanding we add a German subtitle to the original report (English).

The education is done via a slide show, performed exactly the same in every volunteer. The duration of the presentation is about 10 minutes. (Slides are attached at the appendix of this protocol.) The investigator of the treatment interventions is not involved in placebo education prior to intervention.

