- To investigate the effect of education prior to an open label placebo application.
- To investigate the effect of open label placebo application on biomarkers of stress (saliva cortisol)

Outcome(s):

[figure not shown]
Primary outcome:

Pain response measured by the Area under the Pain Curve (AUPC) using the numeric rating scale (NRS) from minute 30 to 100 after inducing definded pain in an experimental setting. Main comparison: The effect of open label placebo v.s. no treatment intervention.

Secondary outcomes:

 The pain response measured by the AUPC (NRS every 10 minutes during electrical stimulation) will be used for further comparison of the two different treatment interventions every participant recieves during the study.

	 Regularly taking medication potentially interfere with pain sensitation (analgesics, antihistamines and calcium and potassium channel blockers) Neuropathy Chronic pain Neuromuscular or psychiatric disease Known or suspected kidney or liver disease 		
Measurements and procedures:	Healthy male adults are recruted via an advertisment on the homepage of the University of Basel. After informed consent, but before any intervention, the participiants are randomized to a placebo educated and a non-educated group. The education group will receive an education about placebos and their effects prior to study intervention during the placebo will be applied. Every participiant will pass trough two interventions with electrical induced pain, defined at a NRS of six for 100 minutes each. Between the sessions a minimal two weeks washout period will be hold. During the two interventions participiants beceive the following treatments delineated above in a randomized manner.		
Study medication/ Study product:	Intravenous application of: open label placebo (2ml saline 0.9%).		
Control intervention	During one intervention (A) we do not apply any treatment at all during the intervention time. This to control for habitation effects during current application and create a comparison.		
Number of Participants with Rationale:	Based on our sample size calculation, we will require 22 participants. Recent estimates state that some 20-30% of patients are placebo-non-responders. Consequently, we will include 29 patients. However, with an estimated drop-out of 10% we plan to recruit 32 paitents. Patients dropping out will be replaced.		

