The duration of the study from the first participant in to the last participant out is 5 months. Duration of an individual participant from T0-T2 (cp. figure 1) will be approximately 2-3 weeks weeks (time from primary assessment with 1st intervention until 2nd intervention).

[figure not shown]

Figure 1: Study time course for a participant. T= time point

Visit	Description	Involved stuff	Duration	
Inclusion/ Randomization/ Education	 Check of inclusion/ exclusion criteria Discussion of open questions prior to study inclusion Obtain written consent Randomization to PEG or nPEG Placebo education depending on randomization 	 Study nurse Investigator not involved in treatment interventions 	Administrative tasks: 30min Placebo education 10-15min	
1 st intervention	 Treatment A-B depending on randomization Application of open label placebo in treatment B (study nurse; investigator not present) Assessment of outcomes (investigator) 	Study nurseInvestigator	Preparation time: 30 min Intervention time: 100 min	
2 nd intervention	 Second treatment (i.e. treatment B if treatment A applied in 1st intervention). Application of open label placebo in treatment B (study nurse; investigator not present) Assessment of outcomes (investigator) 	Study nurseInvestigator	Preparation time: 30 min Intervention time: 100 min	

Table1: Overview of interventions, involved study stuff and time course

1. Administrative structure:

1.1 Sponsor:

Department of Anaesthesia, Surgical Intensive Care, Prehospital Emergency Medicine and Pain Therapy of the University Hospital Basel

1.2 Sponsor investigators:

[name], PD
Head of Pain Unit
Department of Anaesthesiology/ Chronic pain Unit
[name]
[name] CH
[contact]

E-mail: [contact]

1.3 Principal Investigators:

[name] Senior physician Department of Anaesthesiology/ Chronic pain Unit [name] [name] CH

[contact]

E-mail: [contact]

[name], MSc Research Fellow, Department of Anaesthesiology University of Basel (USB) [name] [name] CH

[contact]Fax: [name] E-mail: [contact]

[name], PD Senior Physician Department of Anaesthesiology University of Basel (USB [name] [name] CH [contact]

[contact]

E-mail: [contact]

[name]

Scientific assistant, doctoral candidate

Department of Anaesthesiology University of Basel (USB)

[name] [name] CH [contact] [contact]

E-mail: [contact]

[name], [name] 1 [name]

[contact] [contact]

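### Education is given once before session 1 while session order is randomised, so B1 versus B2 averages over two education-to-placebo intervals and should be balanced on and adjusted for order

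*Combined protocol and SAP*

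**What the plan says.** **Timing of education.** Section 7.4: "The participants randomized to the PEG will receive additionally an education about placebos prior to the first intervention". The visit overview (Table 1, under Study schedule) agrees. It lists "Placebo education depending on randomization" at the inclusion visit, ahead of both sessions, and shows no repeat at either session. The synopsis (Measurements and procedures) is looser and puts the education "prior to study intervention during the placebo will be applied".

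**Order and gap.** Section 7.2 defines the sets (A, B1) and (A, B2) and states that "the individual components of these sets will be randomized"; it adds that "we operate the interventions in a randomized order in every participant". On the gap, the synopsis says: "Between the sessions a minimal two weeks washout period will be hold". The Study schedule puts an individual's participation at about two to three weeks.

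**Analysis.** Section 11.4 compares the AUPC of B1 with that of B2 by a Wilcoxon test and names no covariate. Session order appears in the mixed model described for the first hypothesis (B versus A), where the stated purpose is to allow for habituation within and between sessions. Education is not among that model's terms. The synopsis (Statistical Considerations) says more generally that, besides a simple test for each hypothesis, a mixed-effects model will account for treatment order.

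**The concern.** With education fixed before session 1 and order randomised, the interval between education and placebo is determined by order. A B-first participant hears the slide show and has the placebo in his next session. An A-first participant first goes through 100 minutes of stimulation without treatment, then waits out the washout. The text read aloud before each injection (section 7.10 and appendix) is the same in both education groups, so it does not refresh the education.

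Two things follow for B1 versus B2. First, it estimates an average over a short and a long interval, which is smaller than the short-interval effect if education fades. Second, it compares different people, so a difference between first and second sessions does not cancel within person as it can in B versus A. The plan regards between-session habituation as important enough to model for B versus A, but section 11.4 does not carry that adjustment over to education.

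**Working it through.** **The plan's own figure.** Section 11.2 sizes the trial for A versus B only and gives no figure for education. Its 22 can be reproduced with a paired t-test under assumptions it does not state: difference 50 NRS x min, SD of the difference 60, two-sided 0.05, 90% power. This gives n = 18, and 18 x 1.2 = 21.6, rounded up to 22. Then 22 x 1.3 = 28.6, taken as 29, and 29 x 1.1 = 31.9, taken as 32. Nothing below depends on this reconstruction except the total of 32.

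**Inputs.** From section 11.2: N = 32, SD 60, effect 50 (stated for A versus B and borrowed here for illustration). Assumed: 16 v 16 by education, half of each group A-first, two-sided 0.05. The fraction f of the education effect that survives the gap is unknown.

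**Mixture.** A-first educated participants: 16 x 0.5 = 8. Measured effect = 0.5 x 1 + 0.5 x f = (1+f)/2 of the immediate effect.

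**Power of a two-sample t-test**, noncentrality = effect / (60 x sqrt(2/16)) = effect / 21.2, 30 df, immediate effect 50:

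| f | (1+f)/2 | measured effect | power |
|---|---|---|---|
| 1 | 1.000 | 50 | 63% |
| 0.75 | 0.875 | 43.75 | 51% |
| 0.5 | 0.750 | 37.5 | 40% |
| 0.25 | 0.625 | 31.25 | 30% |
| 0 | 0.500 | 25 | 21% |

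With an immediate effect of 25, power runs from 21% (f = 1) to 9% (f = 0).

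**Chance imbalance of order.** Suppose order were drawn independently for each participant, without blocking. The B-first counts of the two groups of 16 would then differ by 4 or more in about 22% of trials. If AUPC under B differs by s between first and second sessions, a count difference of 4 moves B1 minus B2 by s x 4/16 = s/4 in either direction. The documents give no s.

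**What an analysis by order can show.** With 8 per cell, the difference between the two order-specific education effects has standard error 60 x sqrt(4/8) = 42.4. For an immediate effect of 50 the true difference is 50 x (1-f): 25 at f = 0.5 and 50 at f = 0. Power on 28 df is about 9% and 21%.

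**The case against.** Much of the case on the other side stands.

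- **Conflict between synopsis and section 7.4.** A reader might infer that the documents prescribe two timings. They do not: education before session 1 also precedes the placebo session for everyone, so the synopsis wording is satisfied. It is loose and worth aligning, but it does not contradict section 7.4 or Table 1.
- **Bias.** A reader might infer that the education comparison is biased. It is not: order is randomised in both education groups, so B1 versus B2 validly estimates an effect averaged over the two intervals, and a chance imbalance of order is random error.
- **No order adjustment at all.** The synopsis promise of a mixed model accounting for order can be read as covering education. What is missing is the specification in section 11.4.
- **No balance of order.** Section 7.2 promises balanced assignment of the study groups, and the design figures are not reproduced in the text reviewed. A four-cell layout cannot be ruled out; the text just does not state one.
- **A null result as faded education.** Even with no fading, power is only 63% for an effect of 50 and 21% for 25, so a null result would be hard to interpret in any case.
- **Moving education to just before session B.** This would equalise the interval but at a real price. In A-first educated participants, session A would precede education and session B would follow it, so the primary B versus A contrast would include the change in education status. It would also tell those participants, before calibration, that the placebo session had come. Education before session 1 keeps education status constant within each person and is a defensible choice.

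What the objections do not remove is that the interval is set by order, that B1 versus B2 is between people, and that section 11.4 states no order term for it.

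**Conclusion.** The point holds as a minor one on a secondary comparison. About half of the educated participants (about 8 of 16, given 1:1 allocation and balanced order) receive the placebo at least two weeks later than the others. The planned B1 versus B2 contrast pools them without a stated order term. The consequence is possible dilution by (1+f)/2, plus avoidable noise from session effects and chance imbalance of order. The dilution is hypothetical: no document says that education fades. The interval from education to session 1 is not stated either, but whatever it is, the two orders differ by at least two weeks. The primary comparison is not affected.

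**What to change.** 1. Keep education before session 1, and reword the synopsis to match section 7.4 and Table 1.
2. State that order is randomised in blocks within each education group: four cells of about 8.
3. In section 11.4, include session order as a factor in the B1 versus B2 analysis, for example a linear model of session-B AUPC on education and order. A signed-rank test cannot carry this term and, being a paired test, does not suit a comparison of different people; that is a separate point.
4. Report the B1 versus B2 estimate with its interval separately for B-first and A-first participants, labelled descriptive, given the 9% to 21% power shown above.

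The cost is a four-cell randomisation list, one model term and a few lines of text, with no extra participants, visits or staff. The order factor removes session effects and order imbalance from the contrast. It does not restore any effect lost to fading, so the report should say that the education effect is an average over the two intervals.
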